### Background & Purpose of Research

## Describe the purpose, specific aims or objectives and specify the hypotheses or research questions to be studied:

For this study, we hypothesize that use of movable wheelchair arm rest device during inpatient therapy will lead to significantly greater improvements in UE motor recovery than conventional treatment. (For a demonstration video of the movable wheelchair arm rest device, please visit: <https://youtu.be/RfbaOGhJfug>). Our Aim is to perform a randomized controlled trial of the movable wheelchair arm rest device with inpatients with subacute stroke in three different inpatient rehabilitation facilities (N=58; Months 6-24). UCI will be one of the study sites. Rancho Los Amigos Rehabilitation center and Casa Colina Hospital and Centers for Healthcare will potentially be the other two study sites. We are in the process of negotiating the contracts between sites. Participants will be >3 days and <3 weeks post-stroke, with initial FM scores <4239. Participants will be randomized to receive the movable wheelchair arm rest device or an electronic exercise program and instructed to practice moving their arm between therapy sessions. The primary outcome measure will be change in FM score from baseline to three-months post-stroke. We hypothesize that participants who receive movable wheelchair arm rest device will have significantly greater improvements in FM score than control ( $p < 0.05$ , RM-ANCOVA) without an increase in pain or spasticity, if they exceed the putative threshold of UE motor drive needed for recovery. Success Criteria: A significantly greater increase in FM of >4.25 points (the FM MCID40) between movable wheelchair arm rest device and control at three months.

At project end, we will have validated the clinical feasibility and efficacy of the movable wheelchair arm rest device and optimized it for production and mass distribution. If our plan is successful, we will have demonstrated that wheelchair-based "rocking therapy" can help patients routinely achieve the threshold level of sensory motor drive needed to provoke true UE recovery.

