### **Secondary outcome measures**

Secondary outcome measures will include the change in:

1. Box and Block Test
2. Modified Ashworth Spasticity Scale for shoulder elbow and wrist joints
3. Shoulder subluxation distance in centimeters
4. Visual Analogue Pain scale to assess shoulder, elbow, wrist, and hand pain.
5. Motor Activity Log (MAL) – Post therapy and Follow-up assessments only
6. Functional Ambulation Category (FAC)
7. Number of exercise repetitions performed with device or exercise program.

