## Sample Size Determination:

1. Explain how the overall target sample size was determined (e.g., power analysis; precision estimation). Power analysis should (at least) match the primary outcome/endpoint.
2. Provide justification of the effect size for the primary outcome based on preliminary data, current knowledge/literature and/or cost consideration.
3. If appropriate, provide sample size justification for secondary outcomes.

Based on a power analysis using data from our previous LARA RCT with individuals with subacute stroke (n=19)36, enrolling 29 participants in each group, brings a total of 58 from 2 groups, will provide an 80% chance to demonstrate a significant difference in FM between the device and control at the three-month follow up ( $\alpha = 0.05$ ), assuming a dropout rate of 10%.

---

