All study participants will receive 3 evaluations from a blinded evaluator: baseline at admission to the ARU, at discharge from ARU, and a 3-month post-stroke follow up visit.

Please see attachment for the schedule of study activities.

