## **Describe the statistical methods for the stated specific aims and hypotheses. The analysis plans should match the stated study specific aims and hypotheses:**

All reported data from this study will be disaggregated by sex to test for any potential bias due to this biological variable. Data will be analyzed using modified intention-to-treat analysis. That is, all participants will be included in the analysis if the follow-up assessment is available, regardless of any deviations from the protocol. The effect of treatment on the primary outcome measure will be assessed using a repeated measures analysis of covariance (RM-ANCOVA) to account for any baseline differences between groups or variability in treatment intensity, with follow-up comparisons performed using Bonferroni-corrected t-tests or Wilcoxon rank sum tests if the data violates the assumption of normality. We hypothesize the participants in the movable wheelchair arm rest device group will have significantly greater and clinically meaningful (i.e. >4.25 FM points) reductions in motor impairment than participants in the control group due to the increased dose of UE motor system activation. Using data from the sensors on movable wheelchair arm rest device, we will test if this effect depends nonlinearly on the number of repetitions performed with the device, consistent with recent meta-analyses of forelimb recovery in a rodent model of stroke. That is, we hypothesize that the movable wheelchair arm rest device will provide a benefit only if the dose exceeds a threshold. A key goal is to also identify that threshold (by making a graph for humans like the one for rats), which will enable us to move forward with effective clinical prescription and goal setting with the movable wheelchair arm rest device. Visual analog pain, spasticity, and FAC scores will also be analyzed using RM-ANCOVA to test for significant changes related to use of the device. All analyses will be reviewed by a statistical consultant in the Institute for Clinical and Translational Science at UC Irvine.

**Provide precise definitions of the study endpoints and criteria for evaluation; if the primary outcomes are derived from several measurements (i.e., composite variables) or if endpoints are based composite variables, then describe precisely how the composite variables are derived:**

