The endpoint of the study is 3-month post-stroke follow up visit. The primary outcome measure is the Fugl-Meyer Upper Extremity Motor Assessment Score at the 3-month post-stroke follow-up.

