
Boost is a novel arm rest that clips on a standard wheelchair with standard wheelchair features where anti-tipping bars in the back will prevent the wheelchair from tipping over. We have different sizes of the wheelchairs, 16", 18" and 20", to fit various patients according to their size and weight. We also have adjustable leg rests where we can fit patients with leg lengths or heights. We will have routine maintenance to make sure the wheelchairs operate well and are safe. For all study visits, we will have study personnel or nursing staff at the acute rehab unit present for the patients if patients need any help.

**Specify the total duration of a subject's participation in the study and clearly outline the duration of participation for each study visit and sub-study, as applicable:**

The duration of the subject's participation in the study will be approximately 3 months after the onset of stroke.

**List **all** data collection tools (e.g., measures, questionnaires, observational tool) below; include citations for standardized/validated measure(s):**

- Upper Extremity Fugl-Meyer Motor Score
- Box and Block Test
- Shoulder subluxation distance in centimeters
- Motor Activity Log (Post therapy and follow up assessments)
- Visual analog pain score for the shoulder and hand
- Modified Ashworth Spasticity Scale for elbow and wrist flexors and extensors
- Functional Ambulation Category (FAC)
- NIH Stroke Scale
- Number of exercise repetitions performed with device or exercise program
- Days of inpatient hospitalization stay
- Vital signs (heart rate, blood pressure)

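### The modified intention-to-treat rule is a complete-case rule on the 3-month visit, with no stated missingness assumption, sensitivity analysis or report of missing 3-month FM by arm

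*Combined protocol and SAP*

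**What the plan says.** The statistical methods text in Study Design & Statistics calls the analysis modified intention-to-treat and explains the term: "all participants will be included in the analysis if the follow-up assessment is available, regardless of any deviations from the protocol". It names a repeated-measures ANCOVA for the primary outcome, used "to account for any baseline differences between groups or variability in treatment intensity". The later answer on primary-outcome methods names Bonferroni-corrected t-tests, or Wilcoxon rank sum tests if a normality test fails.

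Three blinded evaluations are scheduled: "baseline at admission to the ARU, at discharge from ARU, and a 3-month post-stroke follow up visit". The endpoint text reads: "The endpoint of the study is 3-month post-stroke follow up visit". The Secondary outcome measures list keeps the discharge and 3-month occasions apart, restricting the Motor Activity Log to "Post therapy and Follow-up assessments only".

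Sample Size Determination plans 29 per group for 80% power, "assuming a dropout rate of 10" percent. The success criterion under Background & Purpose is "A significantly greater increase in FM of >4.25 points" between device and control at three months.

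**The concern.** Whether someone returns at three months is known only after randomisation, and it may depend on how the arm has recovered and on which programme the person was given. Only the evaluators are described as blinded. After discharge one group may keep a device and the other an exercise programme, so reasons for returning could differ by arm. If they do, and if they relate to recovery, the participants who return are no longer a randomised comparison.

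The rule also leaves out a participant who had the discharge evaluation but missed the last visit, although that evaluation is informative about the missing score. The plan expects some loss, yet nothing in it would reveal a distortion of this kind. Success is judged against a fixed 4.25-point threshold, so a shift of a few tenths of a point could matter for an estimate close to it.

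**Working it through.** **1. Which visit the rule refers to.** The endpoint text ties the study endpoint and the primary FM score to the 3-month follow-up. The Motor Activity Log entry and Project Procedures treat the discharge (post-therapy) assessment as a separate occasion. The follow-up assessment in the inclusion rule is therefore the 3-month visit.

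**2. Whether FM is measured at discharge.** The activity schedule is an attachment that is not in the text. The list of data collection tools limits one item by visit, "Motor Activity Log (Post therapy and follow up assessments", and lists FM with no limit. FM at discharge is a reasonable inference, not a stated fact.

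**3. The plan's own figure.** Sample Size Determination gives no effect size or SD, so 29 per arm cannot be fully reproduced. The dropout step can: 26 / (1 − 0.10) = 28.9, rounded up to 29. The plan thus expects 58 × 0.90 = 52.2 evaluable participants, with about 6 missing the visit. For 26 per arm, 80% power and alpha 0.05 (two-sided assumed), a t-test needs d = 0.792. If 4.25 points was the design difference, which the plan does not say, the SD is 4.25 / 0.7923 = 5.36.

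**4. Size of the completers bias.** Every input here is an assumption, because the documents give none:
- residual SD from 5.45 (close to the implied value) to 12;
- correlation r of 0.6 to 0.8 between discharge and 3-month residuals;
- logistic dropout with log-odds slope b of 0.6 to 1.2 per SD of the discharge residual, calibrated to 10% per arm.

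Let m be the mean standardised discharge residual among those who return:

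m = ∫ x φ(x) [1 − p(x)] dx / 0.90, with p(x) = 1 / (1 + exp(−(a − b·x))) and a set so that p averages 0.10.

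Numerical integration gives m = 0.058, 0.083 and 0.105 for b = 0.6, 0.9 and 1.2. If loss is selective in one arm only, bias = SD × r × m:

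| SD | r 0.6, b 0.6 | r 0.7, b 0.9 | r 0.8, b 1.2 |
|---|---|---|---|
| 5.45 | 0.19 | 0.32 | 0.46 |
| 8 | 0.28 | 0.47 | 0.67 |
| 12 | 0.42 | 0.70 | 1.00 |

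- Same mechanism in both arms: the two terms cancel, so the bias is about 0.
- Opposite directions (extreme case): double, 0.38 to 0.91 at SD 5.45 and up to 2.01 at SD 12.
- 3% dropout, one arm: 0.06 to 0.32 across SD 5.45 to 12.
- No missed visits: 0.

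**5. Against the standard error.** With 29/29, SE = SD × √(2/29) = 0.263 × SD. The one-arm ratio is free of the SD: 0.6 × 0.058 / 0.263 = 0.13 up to 0.8 × 0.1045 / 0.263 = 0.32. With 19/18, an assumed split of the 37 enrolled, SE = 0.329 × SD and the ratio is 0.11 to 0.25.

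**6. A separate simulation** (400,000 per arm; true difference 4.25, SD 5.46, slope 1, r 0.5 to 0.85) agrees. With 10% selective loss in the device arm, completers give 4.50 to 4.68, and an estimate using the discharge score gives 4.24 to 4.26. With the same mechanism in both arms, completers give 4.25 to 4.27.

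**7. Limits of the remedy.** If dropout depends on the unseen 3-month value itself, a likelihood model removes only part of the bias. At SD 8, r 0.7, slope 0.9 and opposite directions, it falls from 1.33 to 0.70. The precision gain is negligible (SE 2.26 to 2.23).

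**The case against.** The strongest reply is that little or nothing may be missing. Under Subject Withdrawals the renewal form answers No to removals and to voluntary withdrawals, and its Progress Report says follow-up assessments are complete. The 37 adults equal the three site counts (2 + 12 + 23), so those answers may cover the whole study. Ten percent is a planning figure; at 18 or 19 per arm it is about two people. This stands as a limit on size. It does not settle the matter, because a missed visit is not a withdrawal and the documents do not give the number of 3-month FM scores obtained.

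It can also be said that the plan does handle missing data, since complete-case is a method. That is right. A reader might infer that missing data are not addressed at all, or that every discharge evaluation is discarded. Neither follows: the rule is stated, and discharge scores of those who return can still enter the repeated-measures model. What is absent is an assumption to justify the rule and a check on it.

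The rule says participants are included if the visit is available, not only if. But the sentence explains the word modified, and it would have no effect if people without the visit were included anyway. The clause about deviations guards against per-protocol exclusions, not missing outcomes.

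Finally, changing the primary model when procedures are complete and analysis is under way carries its own risk of data-driven choice. That stands, and it is why the fix depends on whether between-arm results have been seen.

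**Conclusion.** The concern holds as a gap in the plan of modest size. The primary analysis set is conditioned on a post-randomisation event, and nothing planned would show whether that matters. With 10% dropout selective in one arm, the bias is about 0.2 to 0.5 FM points near the implied SD of 5.4, and reaches 1.0 only at SD 12. That is 0.13 to 0.32 of a standard error at 29/29. It is about zero under a common mechanism and zero with no missed visits. These figures rest on assumed SDs, correlations and dropout slopes, and the implied SD rests on 4.25 having been the design difference.

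A reader might infer that the trial's result is biased. The documents do not support that: they show no differential loss, and their status answers point towards little loss. Confidence is medium, mainly because neither the visit schedule nor the count of 3-month scores is available.

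**What to change.** 1. Report missing 3-month FM by arm. If none is missing, the concern had no effect.
2. If the schedule confirms FM at discharge and between-arm results are unseen, replace the inclusion sentence with: *All randomised participants are analysed as randomised in a likelihood-based repeated-measures model of FM using all available discharge and 3-month values, adjusted for baseline FM or its randomisation stratum, with an unstructured covariance and a small-sample degrees-of-freedom correction; the 3-month between-arm contrast is primary.* Name the same model in the primary-outcome methods answer. Keep the completers analysis and the planned Wilcoxon test as sensitivity analyses. Participants with no post-baseline FM add no outcome information, so count them by arm.
3. If between-arm results have been seen, keep the planned completers analysis primary and show the likelihood model beside it, labelled post hoc.
4. If any 3-month FM is missing, add one delta-shift analysis: impute under missing at random, then lower the imputed values by, for example, 4.25 points (floor at 0) in the device arm, then in the control arm. With 3 of 29 missing in one arm this moves the contrast by 4.25 × 3/29 = 0.44 points; with 2 of 18, by 0.47.
5. As a separate point, keep covariates known only after randomisation (treatment intensity in the statistical methods text, length of stay in Project Procedures) out of the primary model and use them only in a supportive one.

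No new data are needed. The costs are a covariance structure estimated on a small sample, the Wilcoxon fallback moved from primary to sensitivity, and a late change that must be dated and disclosed, stating whether it precedes unblinded results.

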## **Describe the primary outcome variable(s), secondary outcome variables, and predictors and/or comparison groups as appropriate for the stated study objectives/specific aims:**

### **Primary outcome measure**

The primary outcome measure will be the change in Fugl-Meyer Arm Motor Assessment Score (FMAMA) from baseline to three-month post-stroke to assess increases in motor recovery of the upper extremity.

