### Exclusion Criteria

- Subarachnoid hemorrhage
- Presence of other neurological or psychological disorders affecting motor functions
- Moderate to severe pain in the stroke-affected upper extremity (score > 6 on 10-point visual analog pain scale), while using the movable wheelchair arm rest device
- Severe tone at the affected upper extremity (score > 4 on the Modified Ashworth Spasticity scale)
- Severe aphasia (score of 2 or higher on the NIH stroke scale – question 9). PI may dismiss this criterion if the participant is deemed able to follow all study instructions
- Deficits in vision, language, attention, neglect or other cognitive functions severe enough to interfere with safe operation of wheelchair or the movable wheelchair arm rest device
- Currently pregnant
- Difficulty in understanding or complying with instructions given by the experimenter
- Inability to perform the experimental task that will be studied

**Is eligibility based on age, gender, pregnancy/childbearing potential, social/ethnic group, or language spoken (e.g., English Speakers only)?**

No, Subject Eligibility is not based on these factors

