**Describe the statistical method(s) that will be used to analyze the primary outcome(s) or endpoints:**

t-tests with Bonferroni corrections, or Wilcoxon rank sum tests if the distributions fail the Lilliefors test for normality.

**If appropriate describe secondary or post hoc analyses of primary outcome(s) or other exploratory analysis and if necessary, provide a breakdown of the methods used per outcome or endpoint:**

The effect of treatment on each outcome measure will be assessed using a repeated-measures ANOVA

---

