## Provide a detailed chronological description of the procedures:

Participants will be invited for an initial assessment within three days of admission to an IRF to confirm they meet the inclusion criteria and to establish a baseline measure. Those who qualify will be randomly assigned to either the movable wheelchair arm rest device group or the control group. To ensure matched levels of impairment between groups, subjects will be stratified by their FM score into two levels (0-21, 22-42) and then randomized by alternating block allocation based on the time of enrollment. Individuals in the device group will be provided with a wheelchair equipped with movable wheelchair arm rest device and trained how to use it to perform stationary reaching practice and to help them ambulate. Once participants are competent, they will be instructed to perform stationary reaching practice and to use the movable wheelchair arm rest device to ambulate around the inpatient facility, with a target dose of 1000 device "reps" per day, which we estimate will take about 30 minutes of device use at around 1 rep every 2 seconds. The supervising therapist will customize the range of motion needed for device's integrated electronics to count a "rep" based on each patient's abilities. Participants in the control group will be given an electronic home exercise program (HEP) of proximal arm exercises developed by study therapists. They will be encouraged to exercise for 30 minutes a day with the electronic HEP (i.e. to match the duration with device). A supervising therapist will check in with all participants once per week to check on engagement with their exercise program and to troubleshoot any issues with device or the electronic exercise program. To measure compliance and quantify dose, the device will report the date, time, and number of repetitions completed for each movement type (stationary/overground) throughout the study using integrated electronics. Using technology, we previously developed for another study, the electronic exercise program provided to control participants will record how long the book is opened each day with a hidden magnetic sensor and data logger. Participants in both groups will continue therapy for the duration of their inpatient stays (average length of stay for individuals with moderate to severe impairment is 14 to 22 days, respectively, based on 104, n = 4142). The actual length of stay for each participant will be quantified and included as a covariate in the data analysis. Once participants are discharged, they will receive a post-therapy assessment and they may be allowed to keep the device and the exercise program based on the therapists' recommendations for the duration of the study. Participants will return three months following stroke onset for a final assessment. We would like to utilize the Tenovi Gateway device to collect the amount of use data. This data will be automatically uploaded to secure web portal through a Tenovi Gateway device, which plugs into the wall at subjects' rooms at the Acute Rehab Unit and or subjects' homes, automatically communicates with the exercise repetition counts through bluetooth, then uploads the data to the web portal through a low-speed cellular data connection. A study team member may visit participants' homes to set up the devices.

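### The NIH Stroke Scale is collected but never named as a covariate; a single pre-specified FM model could use it, for a possible and modest gain in precision

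*Combined protocol and SAP*

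**What the plan says.** The protocol's outcome section defines the primary outcome as the "change in Fugl-Meyer Arm Motor Assessment Score (FMAMA) from baseline to three-month post-stroke". Four places bear on how it is adjusted.

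- Study Design & Statistics, in the answer on statistical methods for the aims, calls for a "repeated measures analysis of covariance (RM-ANCOVA) to account for any baseline differences between groups", and the same sentence adds variability in treatment intensity as a second purpose. The adjustment is described by its purpose; no covariate is listed, and baseline FM is not named.
- The later answer on the method for the primary outcome reads "t-tests with Bonferroni corrections, or Wilcoxon rank sum tests if the distributions fail the Lilliefors test for normality". These tests carry no covariates.
- Project Procedures, in the chronological description, states: "The actual length of stay for each participant will be quantified and included as a covariate in the data analysis". It does not say which analysis. The same description says "subjects will be stratified by their FM score into two levels (0-21, 22-42" before block allocation.
- The list of data collection tools under Project Procedures includes "NIH Stroke Scale" and gives no visit for it. The only other mention is in the Exclusion Criteria, where question 9 alone defines severe aphasia ("score of 2 or higher on the NIH stroke scale"), a criterion the investigator may set aside.

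The schedule of study activities is an attachment that is not part of the public file.

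**The concern.** NIHSS measures overall stroke severity. If its total was recorded before randomisation, it is a candidate prognostic covariate for arm recovery that needs no new data. A covariate of this kind reduces residual variance even when the arms are balanced on it. Describing adjustment as a response to baseline differences leaves room to choose covariates after seeing the imbalance, and a balanced but prognostic score could then be left out.

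The trial has little precision to spare. It planned 58 participants, and the renewal form shows enrolment closed at 37. Any further efficiency has to come from the analysis. The adjusters the plan does mention specifically, length of stay and treatment intensity, are observed after randomisation and may themselves be affected by the assigned arm, so they are not substitutes for a baseline severity score.

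**Working it through.** **Inputs from the documents.** Sample Size Determination: 29 per arm, 58 in total, 80% power, alpha 0.05, 10% dropout. Renewal form: 22 men + 15 women = 37 enrolled, which agrees with 12 + 23 at the two other sites plus 2 at UCI.

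**Not in the documents.** The effect size, the SD, the sidedness of the test, and any correlation of NIHSS with FM. I assume a two-sided test and show a range for NIHSS.

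**The plan's own figure.** 26 / (1 − 0.10) = 28.9, which rounds up to 29 per arm, so the dropout step is consistent with 26 evaluable per arm. The 26 itself cannot be reproduced without an effect size and SD. Back-solving 80% power from the noncentral t distribution with n = 52 and 50 df needs a noncentrality of 2.857. Since noncentrality = d × √n / 2, d = 2 × 2.857 / √52 = 0.792.

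**Reference power at n = 37** (all enrolled assumed evaluable, arms equal): noncentrality 0.792 × √37 / 2 = 2.41 with 35 df gives 64.9%. The SD behind d is treated as the residual SD after baseline FM.

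**Adding NIHSS.** Let R² be the share of that residual variance explained by NIHSS. Two costs are allowed for: one lost degree of freedom (df = n − 3), and chance imbalance of the covariate between arms, which inflates the variance by about 1 + 1/(n − 4). Then

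noncentrality = (d × √n / 2) / √[(1 − R²) × (1 + 1/(n − 4))].

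The inflation is 1 + 1/33 = 1.030 at n = 37 and 1 + 1/48 = 1.021 at n = 52.

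| Assumed R² | n = 37: noncentrality | n = 37: power | n = 52: noncentrality | n = 52: power |
|---|---|---|---|---|
| NIHSS not in model | 2.410 | 65% | 2.857 | 80% |
| 0% | 2.374 | 64% | 2.828 | 79% |
| 3% | 2.411 | 65% | 2.871 | 80% |
| 5% | 2.436 | 66% | 2.901 | 81% |
| 10% | 2.503 | 68% | 2.981 | 83% |
| 15% | 2.575 | 71% | 3.067 | 85% |

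Break-even is about 3% at n = 37 and about 2% at n = 52.

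**Sensitivity to the imbalance allowance.** With only the degree of freedom removed, power at n = 37 is 67.1%, 69.4% and 71.9% for R² of 5%, 10% and 15%, and the cost at R² = 0 is under 0.1 point. The table is the more cautious version.

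**How small R² could be.** Take assumed correlations of 0.6 (baseline FM with outcome), 0.4 (NIHSS with outcome) and 0.5 (NIHSS with baseline FM). The partial correlation is (0.4 − 0.6 × 0.5) / √[(1 − 0.36)(1 − 0.25)] = 0.10 / 0.693 = 0.14, so R² is about 2%. That is below break-even at n = 37 and about at break-even at n = 52.

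**The case against.** The case against is substantial, and most of it limits the point without removing it.

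- A reader might infer that the plan decided against NIHSS, or selects covariates by an imbalance test. The text supports neither. The RM-ANCOVA wording neither includes nor excludes NIHSS, and no selection rule is given. What stands is that NIHSS is not named.
- A reader might infer that a baseline NIHSS total exists for everyone. The list gives no visit, and use of question 9 at screening does not show that a full score was recorded before randomisation. The recommendation has to be conditional on that.
- The gain is assumed. Baseline FM probably carries much of the prognostic information, and the illustrative 2% shows the net effect at n = 37 could be nil or slightly negative.
- There is a prior problem: until the RM-ANCOVA and the unadjusted tests are reconciled, there is no settled primary model for NIHSS to be missing from. This is correct, and it is why the fix starts with one model.
- The renewal form says data analysis is already under way. If the arms have been compared, a covariate added now is a post hoc choice and would have to be labelled as one.

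**Conclusion.** The point holds as an optional improvement in efficiency. No document text gives NIHSS a role in any analysis, and the covariates of the primary comparison are not fixed. Omitting a prognostic covariate does not bias a randomised comparison, so it would be wrong to read this as an error that threatens validity.

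The size is modest: at n = 37, a gain of about 1 to 6 power points if NIHSS explains 5% to 15% of the FM variance left after baseline FM, nothing at 3%, and a loss of about 1 point at 0%. With recruitment closed, interval width is the more useful scale: at 10% explained, the standard error falls by a factor of √(0.90 × 1.030) = 0.963, about 4%.

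These figures rest on the back-solved d of 0.792, a two-sided test, equal arms, all 37 evaluable, and an R² the documents do not supply. The firmer part of the conclusion is that the primary model and its baseline covariates need to be stated once, in advance.

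**What to change.** Before the arms are compared, and if that has not already happened, state one primary model in both places that describe the primary analysis: 3-month FM on arm and baseline FM, plus the NIHSS total if it was recorded before randomisation, each entered whatever the observed balance. With baseline FM in the model, analysing change or the 3-month score gives the same arm difference, so the two outcome definitions in the protocol are both served.

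Keep length of stay and treatment intensity out of this model; the planned analysis of repetitions and response can stay as a separate exploratory analysis. Report the model without NIHSS as a sensitivity analysis. If NIHSS was not recorded before randomisation, the model with arm and baseline FM stands alone.

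Cost: no new data or visits. The NIHSS term needs one sentence and one degree of freedom, with a downside of about 1 power point if it proves uninformative. The wider edit is larger than that: it replaces the repeated-measures model and the unadjusted tests for the primary comparison, names baseline FM explicitly, and removes the two post-randomisation adjusters. If the arms have already been compared, report the NIHSS-adjusted result as post hoc.
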